Denver MOF Score: The appropriate classification and timing of mortality will be captured in the data elements collected as described above. Of similar importance is the morbidity which ensues for those who survive their initial injury. Data elements that include the ability to calculate the Denver post-injury multiple organ failure score⁴⁴⁻⁴⁷ will be collected over the first 7 days for those who are admitted to the ICU > 48 hours. (**Figure 3**) A total score > 3 will be considered MOF and the daily score will be determined up until post-injury day 7 or ICU discharge. Patients not residing in the ICU will be given a score of 0. If data elements are missing on specific days, the individual score for that missing component will be obtained from the prior day's laboratory values.

Dysfunction	Grade 0	Grade 1	Grade 2	Grade 3
Pulmonary PaO ₂ /FiO ₂ ratio	> 300	300 - 201	200 - 101	< 101
Renal Creatinine (umol/L)	<159	160 - 210	211 - 420	> 420
Hepatic Total Bilirubin (umol/L)	< 34	34 – 68	69 - 137	> 137
Cardiac Inotropes	No inotropes	Only one inotrope (small dose)	Any inotrope at moderate dose	Any inotrope at large dose

Figure 3.

Linking Investigations in Trauma and Emergency Services

Task Order 2: Shock, Whole blood and Assessment of TBI (SWAT)

Nosocomial Infection/Sepsis Data Elements: Nosocomial infections and sepsis outcomes will be derived from microbiology records and based upon positive culture evidence including bronchoalveolar specimens, blood cultures, wound cultures, organ space cultures and urinary tract cultures. Over the first 30 days of admission, quantification and location of specimen and classification of organism (Gram+, Gram-, species) will be collected. Quantitative thresholds for ventilator associated pneumonia, catheter related blood stream infections and urinary tract infection will be utilized as determined by the most recent CDC criteria and guidelines (www.cdc.gov/nhsn).

Time to Hemostasis: The time to hemostasis outcome variable will be determined by the ability to reach a nadir transfusion requirement of 1 unit of WB or PRBCs in a 60 minutes time period in the first 4 hours following arrival. Surgeon directed time to hemostasis will also be collected during the case. In the absence of the ability to obtain hemostasis by either of these criteria within the first 4 hours, the patient will be designated a 'non-hemostasis' patient.

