Death from Exsanguination/Hemorrhage: Those patients who succumb on the operating table, IR suite or ICU due to uncontrolled coagulopathy or hemorrhage in the first 4 hours from arrival will have their mortality classified as exsanguination/hemorrhage. This will be determined by the individual trauma surgeon at the time of the event.

Acute Hemolytic Transfusion Reaction: We will utilize and characterize acute hemolytic transfusion reactions as defined by the CDC/National Healthcare Safety Network (NHSN) Hemovigilance Surveillance definition (www.cdc.gov/nhsn).

Linking Investigations in Trauma and Emergency Services

Task Order 2: Shock, Whole blood and Assessment of TBI (SWAT)

Galveston Orientation and Amnesia Test (GOAT): For TBI subjects, we will obtain the GOAT score at the time of discharge and the calculated score per standard methods.⁴⁸ (Figure 4) GOAT is a 10-item questionnaire used to quickly assess post-traumatic amnesia following head injury. The GOAT is read orally to the patient and may be easily administered at the bedside. The total score accounts for orientation of person, place, and time, and recollection of events pre and post-injury. Cutoff scores are available to identify abnormal, borderline, and normal orientation and it will additionally determine if a subject is able to provide continuing participation consent if consented by proxy.

Extended Glasgow Outcome Scale (6 months-GOSE): For TBI subjects, the GOSE score will be obtained at 6 months +/- 1month by hone survey or direct patient contact, whichever is feasible. For those TBI subjects who were unable to consent at discharge, the GOAT will be administered to assess their ability to provide direct consent, prior to the administration of the GOSE. When the assessment is done by phone, the verbal consent of participants who have regained the ability to consent, will be obtained to allow the GOSE to be completed. The score is able to characterize 6 month functional status into 8 well defined categories as shown in (Figure 5).

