Sample Tracking, Management and Storage: After sample obtainment, processing and storage, samples will initially be batched sent to the University of Pittsburgh biological sample repository where it will be tracked, managed and stored until the necessary translational or mechanistic measurement are performed. The CCC and DCC have a long track record of coordinating such processes.

Power Analysis: The prospective cohort study will utilize time to 4 hour mortality for its primary outcome to power the study. Based upon the 6 LITES Network sites admission history that will be utilized and their respective volume of hemorrhagic shock patients meeting inclusion and exclusion criteria and a 3.5 year enrollment time period, we plan to initiate sampling on 1,050 patients over the enrollment time period of the study. With an 85% consent rate which is an estimate based upon prior studies of similar nature, we will consent for participation 892 patients for the study. With an estimate baseline rate of 4 hour mortality of 11.1 % derived from the PROPPR study, there will be 90% power to detect a hazard ratio of 1.9.

Calculations are based on the primary aim of the study based on the following assumptions:

- Type I error rate of 0.05
- Two-sided alternative hypothesis

Linking Investigations in Trauma and Emergency Services

Task Order 2: Shock, Whole blood and Assessment of TBI (SWAT)

- 6 sites will be involved, three whole blood and three component sites
- Each site will enroll 175 participants in 3.5 years of enrollment, of which, 85% will be eligible for the study (149)
- The calculations are based on Cox proportional hazard model
- A 4 hour event rate in the control (non-whole blood) group of 0.111

The power calculations for these secondary aims are presented below. When reporting the results of the analyses, caution will need to be taken with respect to the interpretation of the findings since they are secondary in nature.

The secondary outcomes in Aim 1B include binary outcome, continuous outcomes, and time to event outcomes. For the binary outcomes, the odds ratio that can be detected is presented in Table 1. For the continuous outcome, the effect size that can be detected is 0.13. Finally, for the time to event outcomes, the hazard ratio that can be detected over a range of event rates in the control group is also presented in Table 1.

Event Rate	.1	.2	.3	.4	.5	.6
Odds Ratio	1.76	1.56	1.49	1.46	1.46	1.48
Hazard Rate	2.69	1.70	.37	.30	.27	.30

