Hypothesis#1A: For the primary outcome, the time to death will be generated for each participant. Kaplan-Meier curves will be generated for each treatment group and a log-rank test will be used to compare the distribution of the cumulative proportion. A hierarchical Cox-proportional hazards regression model will be used to control for the within-institution clustering. The hierarchical Cox-proportional hazards regression model will then be used to assess the independent impact of whole blood on time to death after controlling for the clustering effect and potential confounding effects of baseline characteristics. The model will include main effects for whole blood usage and a propensity score for receiving whole blood. The propensity score for the use of whole blood will be generated using a boosted logistic regression model. The dependent variable in the model will be the use of whole blood and the independent variables will be the baseline characteristics of the population. The Cox-proportional hazards model will be used to estimate the cumulative probability of death 4 hours.

Hypothesis#1B: The analytic approach for the secondary outcomes included in Hypothesis#1B will vary based on the type of outcome. For binary outcomes (e.g., 12 hour and 24 hour mortality, death from exsanguination, incidence of MOF, nosocomial infection), the same analytic approach that was carried out for Hypothesis 1a will be implemented.

For continuous outcomes (e.g., transfusion ratios, blood transfusion requirements) a two-sided t-test for correlated means will be used to compare the means between those receiving and not receiving whole blood. A hierarchical analysis of variance model will be used to control for the within-institution clustering. The model will be used to assess the independent impact of whole blood after controlling for the clustering effect and the potential confounding. The model will include main effects for whole blood usage and propensity for receiving whole blood.

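### MOF and nosocomial infection are analysed with no rule for patients who die first; the effect is modest and depends on which reading of the text is applied

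*Combined protocol and SAP*

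**What the plan says.** **Outcome definitions.** Under Specific Outcome Definitions, the Denver MOF Score paragraph gives its purpose as follows: "Of similar importance is the morbidity which ensues for those who survive their initial injury". The score's data elements "will be collected over the first 7 days for those who are admitted to the ICU > 48 hours". A total above 3 counts as MOF, and scoring is daily to day 7 or ICU discharge. The next sentence reads "Patients not residing in the ICU will be given a score of 0". Patients who have died are not excepted. Infection has a longer window: "Over the first 30 days of admission, quantification and location of specimen and classification of organism".

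**Who is in the cohort.** Among deaths, the Exclusion Criteria remove only those in the ED. Other early deaths are expected, since the definition of death from exsanguination covers "Those patients who succumb on the operating table, IR suite or ICU due to uncontrolled coagulopathy or hemorrhage in the first 4 hours".

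**Analysis.** For time to death, Hypothesis#1A says "Kaplan-Meier curves will be generated for each treatment group and a log-rank test will be used", followed by a hierarchical Cox model with a propensity score. Hypothesis#1B puts MOF and infection in a list of binary outcomes that ends "death from exsanguination, incidence of MOF, nosocomial infection), the same analytic approach that was carried out for Hypothesis 1a will be implemented". No section mentions a competing event, cumulative incidence or a cause-specific hazard, or says how to code a death that precedes MOF or infection.

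**Status.** Both outcomes are secondary. On the secondary aims, the Power Analysis adds that "caution will need to be taken with respect to the interpretation of the findings since they are secondary in nature".

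**The concern.** The Hypothesis 1A method was written for death, which nothing can pre-empt. MOF and infection can be pre-empted by death, so the same method needs a rule for patients who die first. The plan gives none, and the score-0 sentence, taken literally, counts a death in the operating room as a patient free of MOF.

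Hypothesis 1B predicts that whole blood lowers both outcomes. If whole blood also lowers early mortality, more severely injured patients survive in that arm and remain at risk of MOF. Two analysts following the text could then report different MOF incidences and, for small differences, a different direction. The choice between them could be made after the data are seen.

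**Working it through.** **The plan's benchmark.** For binary secondary outcomes at a control rate of 0.2, the Power Analysis gives a detectable odds ratio of 1.56. The second rate is 0.2 × 1.56 / (0.8 + 0.2 × 1.56) = 0.312/1.112 = 0.281. A two-proportion calculation (pooled variance, two-sided 0.05, 90% power, 1:1, no continuity correction) needs 589 per arm. The figure therefore reproduces at the 1,190 stated for Aim 1 secondary analyses (595 per arm). At the 892 consented patients (446 per arm), power for the same odds ratio is about 0.80.

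**Inputs.** From the Power Analysis: control 4-hour mortality 0.111, hazard ratio 1.9 and 892 consented. The direction of the 1.9 is not stated; it is taken here as favouring whole blood, as Hypothesis 1A predicts. The documents give no MOF or infection rate, so the MOF risk r among early survivors is an assumption: 0.20, range 0.10 to 0.40. Hazard ratios of 1.5 and 1.3 are also assumptions.

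**Early deaths**

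- Component survival to 4 hours: 1 − 0.111 = 0.889.
- Whole blood survival: 0.889^(1/1.9) = 0.940, so mortality is 0.060.
- Dead by 4 hours with no stated MOF status: 446 × 0.111 + 446 × 0.060 = 49.5 + 26.8 = 76.3 of 892 (8.6%).
- With the one-third whole blood share given under Whole Blood Transfusion Sites: 595 × 0.111 + 297 × 0.060 = 66.0 + 17.8 = 83.9 (9.4%).

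**Reading (a): early deaths score 0.** Crude MOF risk is r × survival. With no whole blood effect on MOF among survivors, r cancels from the risk ratio.

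| Mortality HR | Whole blood survival | Apparent MOF risk ratio |
|---|---|---|
| 1.9 (plan) | 0.940 | 0.940/0.889 = 1.057 |
| 1.5 (assumed) | 0.925 | 1.040 |
| 1.3 (assumed) | 0.913 | 1.028 |

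- At HR 1.9 and r = 0.20: 0.20 × 0.889 = 17.8% (component) against 0.20 × 0.940 = 18.8% (whole blood). The odds ratio is 1.07, or 1.06 to 1.09 for r from 0.10 to 0.40.
- If the true MOF hazard ratio among survivors is 0.80, whole blood survivor risk is 1 − 0.80^0.80 = 0.1635 and crude risk is 0.1635 × 0.940 = 0.1537. The apparent hazard ratio is ln(1 − 0.1537)/ln(1 − 0.1778) = 0.85.

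**Reading (b): deaths stay in the cohort and are censored.**

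- At equal survivor risk the Cox hazard ratio is 1.00, which is correct as a cause-specific ratio.
- 1 minus Kaplan-Meier gives 20.0% in both arms, against whole-cohort incidences of 17.8% and 18.8%.
- Relative overstatement is 1/0.889 = 1.125 (component) and 1/0.940 = 1.064 (whole blood), whatever the value of r, because these deaths precede the event. The same factors apply to infection if deaths are censored.

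**Reading (c): early deaths are outside the scored group.**

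- The 4-hour deaths then cause no overstatement, and 20.0% is the risk among early survivors.
- Only deaths during follow-up matter, and the documents give no mortality figure beyond 4 hours. As an illustration under constant hazards h_M = −ln(1 − r) for MOF and h_D = −ln(1 − d) for death, true incidence is h_M/(h_M + h_D) × [1 − exp(−(h_M + h_D))]. At r = 0.20, an assumed d of 5% gives 19.5% (Kaplan-Meier too high by a factor of 1.025), and an assumed d of 25% gives 17.5% (1.145).

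**The case against.** The case for leaving the text nearly as it is has several parts.

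- **The score-0 sentence probably means patients who left the ICU alive.** The paragraph is about morbidity in survivors, limits data to longer ICU stays and has just mentioned ICU discharge. This stands, and reading (c) is the more natural one. But the sentence has no exception for the dead, and the analysis section does not say which patients enter the MOF comparison.
- **The 12.5% and 6.4% need early deaths inside the analysis set and censored.** This stands; they belong to reading (b) alone.
- **A Kaplan-Meier incidence might never be reported.** MOF and infection are called binary, the Power Analysis uses odds ratios for binary outcomes, and Subgroup Analysis refers to a logistic model even for the primary outcome. This stands as a limit on certainty. Hypothesis#1B nevertheless names the Hypothesis 1A method, and a binary analysis would still need a rule for the dead.
- **The 17.8% and 18.8% appear both as a distortion and as the true incidence.** They are the correct whole-cohort incidences. They mislead only if the gap between them is read as an effect of whole blood on MOF.
- **The effect is small and the plan urges caution.** This is true, but a general caution does not tell an analyst how to code a death.

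A reader might infer that the plan definitely counts early deaths as MOF-free, or that the planned Cox model is invalid. The documents support neither: the text allows three readings, and a Cox model that censors deaths estimates a valid cause-specific hazard ratio.

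**Conclusion.** The concern holds in a limited form. The plan applies a method written for death to two outcomes that death can pre-empt, does not say how those deaths are handled, and has a score-0 rule that does not except the dead.

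- **(a) Early deaths scored 0:** the MOF risk ratio shifts to about 1.06 against whole blood at the design hazard ratio, and to 1.03 to 1.04 at assumed ratios of 1.3 to 1.5. At 20% survivor risk this is 1 percentage point.
- **(b) Deaths kept and censored:** the hazard ratio is sound, but 1 minus Kaplan-Meier overstates incidence by about 12.5% and 6.4% from 4-hour deaths alone.
- **(c) Early deaths outside the scored group:** the result describes early survivors, and any overstatement comes from later deaths that the documents do not quantify.

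The score-0 problem concerns MOF only, and a 0 after death does not erase MOF reached on an earlier day. The Kaplan-Meier problem concerns both outcomes. The figures assume that the 1.9 favours whole blood; if it does not, the shift in (a) reverses. The odds ratio of about 1.07 in (a) is well below the detectable 1.56, but that benchmark rests on 1,190 patients, not 892. A stronger inference, that the study's main conclusion is at risk, is not supported: both outcomes are secondary, the primary outcome is unaffected and mortality is reported separately.

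**What to change.** In the Denver MOF Score paragraph, apply score 0 only to patients who are alive and out of the ICU, and record death before MOF as a competing event.

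In Hypothesis#1B, for MOF and infection:

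- Replace Kaplan-Meier curves with cumulative incidence functions that treat death as a competing event.
- Keep the planned site- and propensity-adjusted Cox model, report it as a cause-specific hazard ratio, and state that deaths are censored.
- Show the cumulative incidence of death beside it.
- State that cumulative incidence still reflects the survival difference (17.8% against 18.8% in the example, with no effect among survivors), so it should not be read alone as an effect on MOF.

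A death-or-MOF composite is optional, as a sensitivity analysis only, because mortality would largely drive it.

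The cost is two wording changes, one extra curve per outcome and a slightly more complex presentation, since the hazard ratio and cumulative incidence must be explained together. Standard software suffices, the Cox model is already planned, and survival is already scheduled in the protocol's data-collection Table 1. No sample size, power figure or primary analysis changes.

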same to research personnel. If obtaining informed consent is not feasible and a legally authorized representative is not reasonably available, the informed consent will be sent via trackable means. The letter will be sent via trackable means and documentation of the addressee and date of mailing and the delivery confirmation with will be kept in the study folder. The subject or their LAR will return the consent using a study provided postage paid envelope. If a signed consent document is not obtained, ~~we don't receive any signed~~ no research activities will be performed nor data will be extracted from the medical record, beyond 36 hours period covered by the Waivers of Consent and HIPAA. Samples and data acquired under those Waivers will be retained.

Whole Blood Transfusion Sites: Busy, Level 1 trauma centers from within the LITES Network will be selected based upon the ability to enroll patients with the proposed inclusion and exclusion criteria who have already implemented or are in the direct process of implementing an urgent release whole blood resuscitation protocol and are able to perform all necessary requirements for the planned prospective cohort study proposed. Those sites with the capabilities to deliver at least 4 units of WB will be selected for participation with preference given to ≥ 6 units urgent release WB capabilities. WB sites will be selected based upon the ability to enroll 33% of patients for the overall cohort study. As WB resuscitation becomes increasingly more widely adopted, there exists the potential to include additional WB sites from within the network as respective institutional practice changes over the 4 year time point of the study. Similarly, there exists the potential to incorporate additional trauma sites into the LITES network based upon their abilities to enroll poly-trauma patients in hemorrhagic shock and the utilization of WB resuscitation. As different trauma sites may utilize differing WB products with different titer levels, matching processes, and leukocyte reducing capabilities, these WB characteristics will be documented for all sites and for all WB units and respective patients enrolled.

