Interim Analysis: There will be two aspects of the interim analysis. First, for efficacy, the Lan and Demets approach will be utilized to conduct the interim efficacy analysis. This approach is preferable over other approaches because it is flexible to the number of interim analyses conducted during the course of the study. The Lan and DeMets approach requires the use of a spending function to allocate the type I error to the interim analysis. The O'Brien and Fleming spending function which minimizes the type I error allocated to the interim analysis, saving the vast majority for the primary analyses will be used. For the proposed interim analysis, assuming that 50% of the study will be completed, it is estimated that the type I error allocated to the interim analysis will be 0.005, leaving 0.048 of the type I error for the primary outcome analysis.

Linking Investigations in Trauma and Emergency Services

Task Order 2: Shock, Whole blood and Assessment of TBI (SWAT)

Time Line: The study will occur over a 4 year period with a 6 month start up period, an interim analysis at 2 years and a 3.5 year enrollment period.

Linking Investigations in Trauma and Emergency Services

Task Order 2: Shock, Whole blood and Assessment of TBI (SWAT)

BIBLIOGRAPHY

3. Hoyt DB. A clinical review of bleeding dilemmas in trauma. *Semin Hematol*. 2004;41(1 Suppl 1):40-43.

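### The 4-hour mortality outcome is sized on patients expected to consent, although it is collected under the waivers, and the primary analysis set is not defined

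*Combined protocol and SAP*

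**What the plan says.** Power Analysis names the outcome that sets the sample size: "The prospective cohort study will utilize time to 4 hour mortality for its primary outcome to power the study". It plans to start sampling on 1,050 patients and then reduces that number: "With an 85% consent rate which is an estimate based upon prior studies of similar nature, we will consent for participation 892 patients". The next sentence states that "there will be 90% power to detect a hazard ratio of 1.9". The list of assumptions makes the same cut per site but calls it eligibility: "Each site will enroll 175 participants in 3.5 years of enrollment, of which, 85% will be eligible for the study (149").

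Recruitment and Consent requests waivers that cover the early blood samples and the extraction of research data for the first 36 hours of admission. Without a signed consent, research activity stops beyond 36 hours, but "Samples and data acquired under those Waivers will be retained". Consent is described as permission to continue: from patients who recover capacity, or from a proxy for those who remain too ill. None of the routes described mentions a patient who has already died.

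Under Analyses, Hypothesis#1A, time to death is generated for each participant. The term is not defined. No section says whether patients without consent belong to the primary analysis, or how deaths before consent are counted.

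**The concern.** Death by 4 hours is the primary event. A patient who dies that early cannot give consent, and consent by others is in practice sought later. Consent is therefore a filter applied after the outcome and probably related to it. Applying 11.1% to the 892 assumes that the two are unrelated.

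An analyst who took the 892 as the analysis set would lose events selectively. The loss may also differ between arms. Whole-blood use follows site (three whole-blood and three component sites), and proxy consent follows state law and local regulations. A propensity score built on baseline characteristics cannot repair selection on the outcome. The same risk applies to 12- and 24-hour mortality, death from exsanguination and early transfusion requirements.

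**Working it through.** **Inputs.** From Power Analysis: 1,050 sampled, 85% consent, 892 consented; 149 of 175 per site; 4-hour event rate 0.111; HR 1.9; Cox model; three sites per arm, so 1:1; "Type I error rate of 0.05"; "Two-sided alternative hypothesis".

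**The reduction.** 1,050 × 0.85 = 892.5, and 6 × 149 = 894. The consent cut and the eligibility cut are the same 85%. It leaves 1,050 − 892 = 158 patients without consent.

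**The stated power.** Schoenfeld's formula for a Cox model at 1:1 is power = Φ(√(D/4) × ln HR − 1.96), with ln 1.9 = 0.642 and D the number of events. Here 11.1% is applied to both arms combined (a flat rate), although the plan gives it as the control rate.

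- 892 patients: D = 892 × 0.111 = 99.0; √24.75 × 0.642 − 1.96 = 1.23; power 89.1%. This is close to the stated 90%.
- 1,050 patients: D = 1,050 × 0.111 = 116.6; √29.14 × 0.642 − 1.96 = 1.50; power 93.4%.

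The Interim Analysis section describes "leaving 0.048 of the type I error for the primary outcome analysis"; using 0.048 changes either figure by less than half a point.

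**Consented-only analysis.** About 117 deaths are expected among 1,050 patients, fewer than the 158 without consent, so an 85% overall rate is compatible with every early death being unconsented. The shares of deaths consented below are assumptions; the documents give none. The total is held at 892, with 1,050 − 116.6 = 933.4 survivors. The third column is (892 − events) / 933.4.

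| 4-hour deaths consented (assumed) | Events left | Survivors consented | Power |
|---|---|---|---|
| 85% | 99 | 85% | 89% |
| 70% | 82 | 87% | 83% |
| 50% | 58 | 89% | 69% |
| 25% | 29 | 92% | 41% |
| 0% | 0 | 96% | none |

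At 50% and 25%, observed mortality among the 892 would be 58.3/892 = 6.5% and 29.1/892 = 3.3%.

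**Differential loss.** Assume no true effect (11.1% in each arm) and 90% of survivors consented. With a share f of deaths consented, observed mortality is 0.111f / (0.111f + 0.889 × 0.9). For f = 0.5 at whole-blood sites this is 0.065; for f = 0.7 at component sites it is 0.089. The apparent HR is ln(1 − 0.065) / ln(1 − 0.089) = 0.72. Exchanging the two shares gives 1.38.

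**The case against.** The strongest reply is that the plan never says it will analyse only consenters, and several places suggest otherwise. Waiver data are retained. Consent governs later procedures. Staff record mortality for up to 4 hours under Screening/Outcome Data and Sample Collection. Power Analysis also uses the word participants for the 175 per site before the 85% is applied. If all 1,050 are analysed, sizing on 892 is merely conservative (89% against 93%).

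This stands, and it rules out three stronger readings:

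- A reader might infer that the plan drops early deaths. It does not say so; this is a risk left open.
- A reader might infer that consent capture does differ by arm. No site consent rates are given and a central IRB is used, so it only may differ.
- A reader might infer that the consent cut leaves the study short of 90% power. With 11.1% strictly as the control rate and a protective HR of 1/1.9, power is 80.0% at 892 and 86.0% at 1,050. The fall from 90% to 80% comes from that reading of the event rate and HR direction. It does not come from consent.

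Nor does the arithmetic prove that 892 underlies the stated 90%. A total of 1,050 with 33% whole blood (the share given under Whole Blood Transfusion Sites) and a flat 11.1% gives 90.3%; 1,190 at 1:1 with HR 1/1.9 gives 89.9%.

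The reply does not supply a definition. In the text, the 90% follows directly from the 892, and the assumptions list treats only 85% as eligible.

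**Conclusion.** The concern holds as an undefined primary analysis set combined with a power statement tied to a subset chosen after the outcome. If every waiver-enrolled patient is analysed, nothing is lost: the study gains 158 patients and about 4 points of power (89% to 93%). If only consenters are analysed, the loss could be severe: 69% power if half the 4-hour deaths are consented and 41% if a quarter are, with possible bias in either direction. These figures rest on a flat 11.1%, HR 1.9, 1:1 allocation, two-sided 0.05, no clustering by site and assumed consent shares. The conclusion that the set must be defined rests on none of them.

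**What to change.** 1. State in the SAP that the primary analysis, and every outcome ascertained within 36 hours, includes all eligible patients enrolled under the waiver regardless of later consent. Say explicitly that deaths before consent count as events.
2. Restate the primary power on that number, after reconciling the totals now in the plan: 892, 894 (6 × 149), 1,050, and the 1,190 given for Aim 1 in the secondary-analysis list. Say whether the 85% is consent or eligibility.
3. Apply the consent reduction only to data that must be collected after 36 hours. Carry deaths known within 36 hours into later outcomes such as 28-day mortality and, in the TBI subgroup, 6-month GOS-E, where death is category 1. Limiting those outcomes to consenters would lose the same early deaths again.

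The cost is SAP wording and a restated sample size; no new data are needed. The downside is that later outcomes will combine all known early deaths with consented survivors only, which tends to overstate later mortality. The SAP should say so and report the number of survivors without consent by arm.

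### For the mortality benefit in Hypothesis 1A, the listed inputs give about 80% power at 892 patients and 86% at 1,050, not 90%; the power section also mixes 892 with 1,190

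*Combined protocol and SAP*

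**What the plan says.** All the primary figures are in the Power Analysis section. On numbers: "we plan to initiate sampling on 1,050 patients over the enrollment time period of the study". The reduction applied to that total is introduced so: "With an 85% consent rate which is an estimate based upon prior studies of similar nature". The number left after it is given in these words: "we will consent for participation 892 patients for the study". The power claim follows: "there will be 90% power to detect a hazard ratio of 1.9".

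The assumptions listed beneath it are a two-sided 5% test, a Cox model, and these two:

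- "6 sites will be involved, three whole blood and three component sites"
- "A 4 hour event rate in the control (non-whole blood) group of 0.111"

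Each site is to enrol 175, "of which, 85% will be eligible for the study (149" per site). The 85% that was a consent rate in the paragraph above has become an eligibility rate.

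For secondary outcomes, "For the binary outcomes, the odds ratio that can be detected is presented in Table 1". The closing bullet of the section then gives 1,190 as the Aim 1 sample size and 417 as the number with traumatic brain injury (TBI), at 35%.

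Three other sections bear on this:

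- Hypothesis #1A expects lower 4-hour mortality with whole blood.
- Whole Blood Transfusion Sites says those sites are chosen for their ability to enrol 33% of the cohort.
- Recruitment and Consent seeks a waiver to extract record data for the first 36 hours, and keeps those data when consent is never obtained.

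**The concern.** A hazard ratio of 1.9 and its inverse, 0.53, have the same log magnitude, but they do not produce the same number of deaths. With 11.1% dying in the control group, a benefit leaves far fewer events than a harm, so power depends on the direction. The plan's hypothesis is a benefit, and its text does not say which direction the calculation used.

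The section also uses sample sizes that cannot all be right. Six sites of 175 make 1,050, so 1,190 is more than the study plans to sample. If the power statements rest on 1,190, they describe a larger study than the one planned. A reader could not then tell what the study is powered for, on the primary endpoint or on the secondary ones.

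**Working it through.** **Inputs.** From the Power Analysis: control 4-hour rate 0.111; two-sided 0.05 (z = 1.96); three against three sites, so whole-blood share w = 0.5; N = 892, 1,050 or 1,190. From Whole Blood Transfusion Sites: w = 0.33 as the alternative. From Hypothesis #1A: the direction is benefit.

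**Sample sizes.** 6 × 175 = 1,050. 0.85 × 1,050 = 892.5, and 6 × 149 = 894. 0.35 × 1,190 = 416.5, the printed 417; 0.35 × 1,050 = 367.5; 0.35 × 892 = 312. The figure 1,190 equals 8 × 175 × 0.85, but no section mentions eight sites.

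**Primary power, benefit direction (Schoenfeld).**

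- HR = 1/1.9 = 0.526, so the whole-blood rate is 1 − (1 − 0.111)^0.526 = 0.060.
- Deaths D = N × [w × 0.060 + (1 − w) × 0.111]. At w = 0.5 this is N × 0.0855.
- Power = Φ(√(D·w·(1 − w)) × |ln HR| − 1.96), with |ln HR| = 0.642.
- At N = 892: D = 76.3; √(76.3 × 0.25) = 4.37; 4.37 × 0.642 − 1.96 = 0.84; Φ = 0.800.

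The simulations used exponential times to death, censoring at 4 hours, a two-sided log-rank test and 40,000 runs. Type I error at 892 was 0.050 at both shares.

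| N | Deaths, 1:1 | Schoenfeld, 1:1 | Simulated, 1:1 | Simulated, 33% whole blood | HR detectable at 90%, 1:1 |
|---|---|---|---|---|---|
| 892 | 76.3 | 80.0% | 78.4% | 70.6% | 0.47 |
| 1,050 | 89.8 | 86.0% | 84.6% | 78.3% | 0.50 |
| 1,190 | 101.8 | 89.9% | 88.9% | 83.6% | 0.526 = 1/1.90 |

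The requirement for 90% is D = (1.96 + 1.282)² / (0.25 × 0.642²) = 102.0 deaths, and 102.0 / 0.0855 = about 1,193 patients. At a 33% share Schoenfeld gives 79.0% (892) and 85.1% (1,050), some 7 to 8 points above simulation, so simulation is the better guide there.

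**Other readings of the same sentence (Schoenfeld).**

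- Harm, HR 1.9: the whole-blood rate is 0.200. At 892 this gives 138.9 deaths and 96.6% power (1:1), or 92.2% (33% share).
- 0.111 as the whole-cohort rate: 892 × 0.111 = 99.0 deaths, power 89.1% (1:1). At 1,050 it is 93.4% (1:1) or 90.3% (33% share).

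**Odds-ratio row.** Take control rate p, q = OR·p / (1 − p + OR·p), n = N/2 per group, and p̄ the mean of p and q. For the pooled two-proportion test, power = Φ[(|q − p|√n − 1.96√(2p̄(1 − p̄))) / √(p(1 − p) + q(1 − q))]. Solving for 90% power:

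| Control rate | 0.1 | 0.2 | 0.3 | 0.4 | 0.5 | 0.6 |
|---|---|---|---|---|---|---|
| Printed | 1.76 | 1.56 | 1.49 | 1.46 | 1.46 | 1.48 |
| N = 1,190 | 1.76 | 1.56 | 1.49 | 1.46 | 1.46 | 1.48 |
| N = 1,050 | 1.82 | 1.60 | 1.52 | 1.50 | 1.50 | 1.52 |
| N = 892 | 1.90 | 1.66 | 1.58 | 1.55 | 1.55 | 1.58 |

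The printed odds ratios have 79.8% to 80.6% power at 892. They reproduce only as increases over the control rate.

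**The case against.** The shortfall depends on a direction that the power section does not state. Its odds ratios are above 1 and work only upward, so 1.9 may also have been computed upward. A two-sided detectable effect printed that way does not in itself contradict Hypothesis 1A.

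The printed 1.9 has one decimal, and 892 can reach it by other routes. With 0.111 as the overall event probability, the hazard ratio detectable at 90% is 1.92 (1:1). In the upward direction, with a 33% whole-blood share, it is about 1.86. Nor does everything secondary confirm 1,190. The printed hazard-ratio row does not reproduce there, although its text may be damaged. The continuous effect size of 0.13 does not either (1,190 gives a standardised difference of 0.188, or f = 0.094). The 33% is a site-selection criterion, not a declared allocation. Finally, because data from the 36-hour waiver are kept, 1,050 is a reasonable analysis set for a 4-hour endpoint.

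Much of this stands. The origin of 90% cannot be established, and the match at 1,190 is suggestive only. But the first route contradicts the bullet assigning 0.111 to controls. The second abandons the three-to-three split and the direction of Hypothesis 1A. Figures that fail at 1,190 add to the need to recompute, because the section itself names that size for Aim 1. Study Setting and Whole Blood Transfusion Sites allow further sites, but the power section assumes six. None of these points removes the conflict between 892 or 1,050 and 1,190.

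**Conclusion.** The concern holds. The sample-size conflict needs no assumption: the primary paragraph plans for 892 or 1,050, while the secondary calculations state 1,190 and their odds ratios and TBI count match it.

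The power shortfall is conditional on 1.9 being the inverse of the Hypothesis 1A benefit and on 0.111 being the control-group rate. Power is then about 80% at 892 and 86% at 1,050 with equal groups, and about 71% and 78% (simulated) at a 33% whole-blood share. Which N applies depends on what the 85% means. If it is consent, 4-hour mortality could be analysed in 1,050; if it is eligibility, in 892 to 894. At the interim-adjusted final level of 0.048 the 1:1 figures are 79.6% and 85.6%.

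All these figures precede any allowance for clustering by site or propensity adjustment. Both are planned and would normally lower power, and the plan gives no intraclass correlation with which to size the loss. This should be fixed; it does not undermine the design.

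**What to change.** 1. State the hazard ratio as whole blood over component (below 1) and confirm that 0.111 is the control-group rate.
2. Use one site count, one N and one whole-blood share throughout. Reconcile 892 and 1,050 with 1,190 and 417, and the three-to-three split with 33%.
3. Say whether 85% is a consent rate or an eligibility rate.
4. State that 4-hour mortality is analysed in all eligible enrolled patients whose data are retained under the 36-hour waiver. Confirm that the propensity-score covariates can be collected under it for patients who never consent.
5. Replace the 90% claim with the power for that set. For HR 0.53 at 1:1 this is about 86% (1,050, if 85% is consent) or 80% (892 to 894, if it is eligibility). At a 33% share use simulation: about 78% and 71%. Label the figure as before clustering and propensity adjustment, or add a stated allowance.
6. Recompute the odds ratios, the other secondary detectable effects and the TBI count on the same N (TBI about 312 if N is 892).

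The cost is a rewritten power section, a recomputed table, one sentence on the analysis set and one check of the waiver's coverage. If the covariates cannot be collected without consent, the adjusted analysis falls back to about 892. No patients are added; the other cost is a less favourable stated power.
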